5.1.2.2 Objective response rate

Objective response rate is defined as the percentage of patients achieving a sCR, CR, PR and VGPR and will be evaluated according to the response criteria of the International Myeloma Working Group (IMWG, 2006; [Appendix 10.1](#)).

- Stringent complete response (sCR)
CR as defined below plus normal FLC ratio and absence of clonal cells in bone marrow by immunohistochemistry or immunofluorescence.
- Complete response (CR)
Complete response is defined as negative immunofixation on the serum and urine and disappearance of any soft tissue plasmacytomas and < 5% plasma cells in bone marrow.
- Very good partial response (VGPR)
Serum and urine M-protein detectable by immunofixation but not on electrophoresis or > 90% reduction in serum M-protein plus urine M-protein level < 100 mg/24 h.
- Partial response (PR)
Partial response is defined as a > 50% reduction of serum M-protein and reduction in 24 hours urinary M-protein by >90% or to < 200 mg/24 h.

Proprietary confidential information.

© 2018 Boehringer Ingelheim International GmbH or one or more of its affiliated companies. All rights reserved.

This document may not - in full or in part - be passed on, reproduced, published or otherwise used without prior written permission.

If the serum and urine M-protein are unmeasurable a > 50% decrease in the difference between involved and uninvolved FLC levels is required in place of the M-protein criteria.

If serum and urine M-protein are not measurable, and serum free light assay is also not measurable, a > 50% reduction in plasma cells is required in place of M-protein, provided baseline bone marrow plasma cell percentage was > 30%.

In addition to the above listed criteria, if present at baseline, a > 50% reduction in the size of soft tissue plasmacytomas is also required.

5.1.2.3 Duration of response (DOR)

The duration of response (DOR) is calculated from the time of first recorded achievement of a response level, that is sCR, CR, PR and VGPR until documented progression or death.

5.1.2.4 Minimal Residual Disease (MRD) response

MRD Response is defined as < 1 tumour cell within 10^4 normal cells in bone marrow using FACS analysis.

MRD response rate is calculated by the percentage of patients achieving MRD response.

5.1.2.5 Duration of MRD response

Duration of MRD response is calculated from the time of first recorded achievement of a MRD response to progression or death.

5.1.2.6 Progression

Progression is defined as an increase of > 25% from lowest response value in any one or more of the following:

- Serum M-component and/or (the absolute increase must be > 0.5 g/dL)
- Urine M-component and/or (the absolute increase must be > 200 mg/24 h)

Only in patients without measurable serum and urine M-protein levels; the difference between involved and uninvolved FLC levels. The absolute increase must be > 10 mg/dL

- Bone marrow plasma cell percentage; the absolute percentage must be > 10%
- Definite development of new bone lesions or soft tissue plasmacytomas or definite increase in the size of existing bone lesions or soft tissue plasmacytomas
- Development of hypercalcaemia (corrected serum calcium > 11.5 mg/dL or 2.65 mmol/L) that can be attributed solely to the plasma cell proliferative disorder

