3.3.4 Removal of patients from therapy or assessments

3.3.4.1 Removal of individual patients

The investigator or patient themselves may stop treatment at any time for safety or personal reasons.

- The patient withdraws consent for study treatment or study participation, without the need to justify the decision.
- The patient needs to take concomitant drugs that interfere with the investigational product (See [Section 4.2](#)).
- The patient can no longer be treated with trial medication for other medical reasons (such as surgery, adverse events, other diseases, or pregnancy)
- Relapse or Progressive Disease (PD), including deterioration of general condition due to disease progression or relapse (for definition see [Appendix 10.1](#)) or start of further anti-cancer therapy
- The patient fails to follow protocol requirements/directions and represent a safety issue for patient

Proprietary confidential information.

© 2018 Boehringer Ingelheim International GmbH or one or more of its affiliated companies. All rights reserved.

This document may not - in full or in part - be passed on, reproduced, published or otherwise used without prior written permission.

- Eligibility criteria are violated and represent a safety issue for patient
- AEs that cannot be managed by dose reduction or adequate treatment
- Further dose reductions considered necessary but not allowed according to the protocol (see [Section 4.1.4.3](#))
- The patient is found to be pregnant during program participation (please refer to [Section 5.2.3](#))
- A change in the patient's status creating an unfavourable risk/benefit in favour to stop study medication.

Given the patient's agreement, the patient will undergo the procedures for early treatment discontinuation and follow up as outlined in the [Flow chart](#) and [Section 6.2](#). For all patients the reason for withdrawal (e.g. adverse event) must be recorded in the eCRF. These data will be included in the trial database and reported.

For safety reasons it is recommended that the patient is encouraged to return for at least the follow-up visit.

When discontinuation is due to a serious AE (SAE) the treating investigator must follow the event until it is resolved, becomes chronic, or remains stable with no resolution expected.

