10. APPENDICES

10.1 INTERNATIONAL MYELOMA WORKING GROUP (IMWG) UNIFORM RESPONSE CRITERIA FOR MULTIPLE MYELOMA

| Response | IMWG criteria ¹ |
|----------------------------------|---|
| sCR | CR as defined below plus normal FLC ratio and absence of clonal cells in bone marrow ² by immunohistochemistry or immunofluorescence ³ |
| CR | Negative immunofixation on the serum and urine and disappearance of any soft tissue plasmacytomas and < 5% plasma cells in bone marrow ³ |
| VGPR | Serum and urine M-protein detectable by immunofixation but not on electrophoresis or > 90% reduction in serum M-protein plus urine M-protein level < 100 mg/24 h |
| PR | > 50% reduction of serum M-protein and reduction in 24 hours urinary M-protein by >90% or to < 200 mg/24 h If the serum and urine M-protein are unmeasurable, ⁵ a > 50% decrease in the difference between involved and uninvolved FLC levels is required in place of the M-protein criteria If serum and urine M-protein are not measurable, and serum free light assay is also not measurable, > 50% reduction in plasma cells is required in place of M-protein, provided baseline bone marrow plasma cell percentage was > 30% In addition to the above listed criteria, if present at baseline, a > 50% reduction in the size of soft tissue plasmacytomas is also required |
| SD | Not meeting criteria for CR, VGPR, PR, or progressive disease |
| Progressive disease ⁴ | Increase of > 25% from lowest response value in any one or more of the following: Serum M-component and/or (the absolute increase must be > 0.5 g/dL) ⁵ Urine M-component and/or (the absolute increase must be > 200 mg/24 h) Only in patients without measurable serum and urine M-protein levels; the difference between involved and uninvolved FLC levels. The absolute increase must be > 10 mg/dL Bone marrow plasma cell percentage; the absolute percentage must be > 10% ⁶ Definite development of new bone lesions or soft tissue plasmacytomas or definite increase in the size of existing bone lesions or soft tissue plasmacytomas Development of hypercalcaemia (corrected serum calcium > 11.5 mg/dL or 2.65 mmol/L) that can be attributed solely to the plasma cell proliferative disorder |

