| Relapse | Clinical relapse requires one or more of: Direct indicators of increasing disease and/or end organ dysfunction (CRAB features) ⁵ . It is not used in calculation of time to progression or progression-free survival but is listed here as something that can be reported optionally or for use in clinical practice Development of new soft tissue plasmacytomas or bone lesions |

Proprietary confidential information.

© 2018 Boehringer Ingelheim International GmbH or one or more of its affiliated companies. All rights reserved.

This document may not - in full or in part - be passed on, reproduced, published or otherwise used without prior written permission.

| | |
|---|--|
| | Definite increase in the size of existing plasmacytomas or bone lesions. A definite increase is defined as a 50% (and at least 1 cm) increase as measured serially by the sum of the products of the cross-diameters of the measurable lesion Hypercalcemia (> 11.5 mg/dL) [2.65 mmol/L] Decrease in haemoglobin of > 2 g/dL [1.25 mmol/L] Rise in serum creatinine by 2 mg/dL or more [177 mmol/L or more] |
| Relapse from CR5 (To be used only if the end point studied is DFS) ⁷ | Any one or more of the following: Reappearance of serum or urine M-protein by immunofixation or electrophoresis Development of > 5% plasma cells in the bone marrow ⁶ Appearance of any other sign of progression (i.e., new plasmacytoma, lytic bone lesion, or hypercalcaemia) |

¹Adapted from Durie BGM, et al. Leukemia 2006; 20: 1467-1473 ([R14-4478](#)); and Kyle RA, Rajkumar SV. Leukemia 2009; 23:3-9 ([R15-0269](#)).

Note: A clarification to IMWG criteria for coding CR and VGPR in patients in whom the only measurable disease is by serum FLC levels: CR in such patients is defined as a normal FLC ratio of 0.26–1.65 in addition to CR criteria listed above. VGPR in such patients is defined as a >90% decrease in the difference between involved and uninvolved free light chain (FLC) levels.

² Confirmation with repeat bone marrow biopsy not needed.

³ Presence/absence of clonal cells is based upon the kappa/lambda ratio. An abnormal kappa/lambda ratio by immunohistochemistry and/or immunofluorescence requires a minimum of 100 plasma cells for analysis. An abnormal ratio reflecting presence of an abnormal clone is kappa/lambda of > 4:1 or < 1:2.

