⁴ All relapse categories require two consecutive assessments made at any time before classification as relapse or disease progression and/or the institution of any new therapy. In the IMWG criteria, CR patients must also meet the criteria for progressive disease shown here to be classified as progressive disease for the purposes of calculating time to progression and progression-free survival. The definitions of relapse, clinical relapse and relapse from CR are not to be used in calculation of time to progression or progression-free survival.

⁵ For progressive disease, serum M-component increases of ≥ 1 gm/dL are sufficient to define relapse if starting M-component is ≥ 5 g/dL.

⁶ Relapse from CR has the 5% cut-off versus 10% for other categories of relapse.

⁷ For purposes of calculating time to progression and progression-free survival, CR patients should also be evaluated using criteria listed above for progressive disease.

Proprietary confidential information.

© 2018 Boehringer Ingelheim International GmbH or one or more of its affiliated companies. All rights reserved.

This document may not - in full or in part - be passed on, reproduced, published or otherwise used without prior written permission.

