10.3 DEFINITIONS OF LABORATORY AND CLINICAL TUMOR LYSIS SYNDROM

| Metabolic Abnormality | Criteria for Classification of Laboratory Tumor Lysis Syndrome | Criteria for Classification of Clinical Tumor Lysis Syndrome |
|----------------------------------|---|--|
| Hyperuricemia | Uric acid >8.0 mg/dl (475.8 μ mol/liter) in adults or above the upper limit of the normal range for age in children | |
| Hyperphosphatemia | Phosphorus >4.5 mg/dl (1.5 mmol/liter) in adults or >6.5 mg/dl (2.1 mmol/liter) in children | |
| Hyperkalemia | Potassium >6.0 mmol/liter | Cardiac dysrhythmia or sudden death probably or definitely caused by hyperkalemia |
| Hypocalcemia | Corrected calcium <7.0 mg/dl (1.75 mmol/liter) or ionized calcium <1.12 (0.3 mmol/liter) [†] | Cardiac dysrhythmia, sudden death, seizure, neuromuscular irritability (tetany, paresthesias, muscle twitching, carpopedal spasm, Trousseau's sign, Chvostek's sign, laryngospasm, or bronchospasm), hypotension, or heart failure probably or definitely caused by hypocalcemia |
| Acute kidney injury [‡] | Not applicable | Increase in the serum creatinine level of 0.3 mg/dl (26.5 μ mol/liter) (or a single value >1.5 times the upper limit of the age-appropriate normal range if no baseline creatinine measurement is available) or the presence of oliguria, defined as an average urine output of <0.5 ml/kg/hr for 6 hr |

*In laboratory tumor lysis syndrome, two or more metabolic abnormalities must be present during the same 24-hour period within 3 days before the start of therapy or up to 7 days afterward. Clinical tumor lysis syndrome requires the presence of laboratory tumor lysis syndrome plus an increased creatinine level, seizures, cardiac dysrhythmia, or death.

[†]The corrected calcium level in milligrams per deciliter = measured calcium level in milligrams per deciliter + 0.8 × (4 – albumin in grams per deciliter).

[‡]Acute kidney injury is defined as an increase in the creatinine level of at least 0.3 mg per deciliter (26.5 μ mol per liter) or a period of oliguria lasting 6 hours or more. By definition, if acute kidney injury is present, the patient has clinical tumor lysis syndrome.

Proprietary confidential information.

© 2018 Boehringer Ingelheim International GmbH or one or more of its affiliated companies. All rights reserved.

This document may not - in full or in part - be passed on, reproduced, published or otherwise used without prior written permission.

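### The hypercalcaemia limit for progression is printed as 11.5 mg/dL or 2.65 mmol/L, two calcium levels about 8% apart by the protocol's own conversion

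*Protocol*

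**What the plan says.** Section 5.1.2.6 of the protocol gives several alternative criteria for progression. One is new hypercalcaemia with no cause other than the myeloma, at "corrected serum calcium > 11.5 mg/dL or 2.65 mmol/L". The progressive disease row of Appendix 10.1 has the same wording: "Development of hypercalcaemia (corrected serum calcium > 11.5 mg/dL or 2.65 mmol/L". The clinical relapse row of that appendix gives the second figure in square brackets: "Hypercalcemia (> 11.5 mg/dL) [2.65 mmol/L".

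Three other places bear on how the criterion is used:

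- **Confirmation.** Appendix 10.1, footnote 4: "All relapse categories require two consecutive assessments made at any time before classification as relapse or disease progression".
- **Role of the relapse row.** Appendix 10.1 says of clinical relapse: "It is not used in calculation of time to progression or progression-free survival".
- **Stopping treatment.** Section 3.3.4.1 lists among the reasons for removal "Relapse or Progressive Disease (PD), including deterioration of general condition due to disease progression or relapse", and points to Appendix 10.1 for the definition.

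The protocol has one other calcium limit printed in both units, in the tumour lysis table of Appendix 10.3: "Corrected calcium <7.0 mg/dl (1.75 mmol/liter". SAP Section 7.5.2 takes progression as given and states no calcium limit.

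**The concern.** A threshold printed in two units should describe one concentration. This pair does not agree with the calcium conversion used in Appendix 10.3, and nothing in the protocol or SAP says which figure takes precedence. A patient whose corrected calcium lies between the two could be called progressed or not progressed, depending on which number the assessor reads.

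Progression is the event that ends PFS, duration of response and duration of MRD response, and it is a reason to stop study treatment. Results are tabulated by dose group, and most planned cohorts hold 3 to 6 patients. One patient classified differently is therefore 17% (1/6) to 33% (1/3) of such a cohort.

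The relapse row does not feed PFS. Section 3.3.4.1 does list relapse as a reason for removal, so the faulty pair there can still bear on discontinuation.

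**Working it through.** **Inputs**

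- Progression limit: 11.5 mg/dL, paired with 2.65 mmol/L (Section 5.1.2.6; Appendix 10.1).
- Protocol's own calcium pair: 7.0 mg/dL = 1.75 mmol/L (Appendix 10.3).
- Albumin correction, given only for tumour lysis syndrome (Appendix 10.3, footnote): corrected = measured + 0.8 × (4 − albumin), calcium in mg/dL and albumin in g/dL.

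**Does the printed pair reproduce?**

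Factor from Appendix 10.3: 1.75 / 7.0 = 0.25 mmol/L per mg/dL, or 4.0 mg/dL per mmol/L.

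- 11.5 × 0.25 = 2.875 mmol/L, not 2.65.
- 2.65 / 0.25 = 10.6 mg/dL, not 11.5.
- The printed pair would need 11.5 / 2.65 = 4.34 mg/dL per mmol/L.

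**Size of the gap**

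11.5 − 10.6 = 0.9 mg/dL, or 2.875 − 2.65 = 0.225 mmol/L. That is 0.9 / 11.5 = 7.8% of the higher value and 0.9 / 10.6 = 8.5% of the lower.

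**Can rounding explain it?**

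| Rounding of the 7.0 / 1.75 pair | Factor (mmol/L per mg/dL) | 11.5 mg/dL equals | 2.65 mmol/L equals | Gap, % of 11.5 |
|---|---|---|---|---|
| 1.745 / 7.05 (lowest) | 0.2475 | 2.85 mmol/L | 10.71 mg/dL | 6.9% |
| 1.75 / 7.0 (as printed) | 0.2500 | 2.875 mmol/L | 10.60 mg/dL | 7.8% |
| 1.755 / 6.95 (highest) | 0.2525 | 2.90 mmol/L | 10.49 mg/dL | 8.7% |

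Rounding the progression pair itself as favourably as possible does not close the gap either: 11.45 / 4.0 = 2.8625 mmol/L, against 2.655 mmol/L. As an outside check, assuming an atomic mass of 40.078 for calcium (4.0078 mg/dL per mmol/L), 11.5 mg/dL is 2.869 mmol/L and 2.65 mmol/L is 10.62 mg/dL.

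**Was one limit intended?**

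The square brackets in the relapse row suggest so. The same row brackets 177 after a creatinine rise of 2 mg/dL. Appendix 10.3 pairs 0.3 mg/dL creatinine with 26.5 µmol/L, and 2 × 26.5 / 0.3 = 176.7. So the bracketed creatinine number is a unit conversion, although its unit is printed as mmol/L.

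**Worked case**

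Measured calcium 10.2 mg/dL, albumin 3.0 g/dL, assuming the Appendix 10.3 correction is the one to use:

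- Corrected calcium = 10.2 + 0.8 × (4 − 3.0) = 11.0 mg/dL.
- In SI units, 11.0 × 0.25 = 2.75 mmol/L.
- 2.75 is above 2.65, so the mmol/L limit is met; 11.0 is below 11.5, so the mg/dL limit is not.

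**The case against.** The strongest reply is that this will seldom matter. The calcium must newly rise into a band 0.9 mg/dL wide, have no cause but myeloma and be confirmed on two consecutive assessments, and no other criterion may already have shown progression. The endpoints are secondary and untested. Investigators may stop treatment on their own judgement, so the calcium limit will rarely decide discontinuation. All of this stands. It limits the consequence but does not make the pair right.

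Two readings might rescue the text.

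- **11.5 mg/dL is the criterion and 2.65 a bad conversion.** The relapse-row layout and the conventional units of the other serum and urine limits favour this. But Section 5.1.2.6 joins the figures with *or* and never says so, and a site working in mmol/L would apply the printed 2.65.
- **Either number suffices.** Then 2.65 mmol/L always triggers first and 11.5 mg/dL has no effect. A site reading the mg/dL figure would still use a higher limit.

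Disagreement between sites is not shown. Calcium is measured locally, about 5 sites are planned and no reporting unit is stated. Appendix 10.4 does allow for differing local units in the creatinine clearance formula. If every site uses one unit, a single limit applies throughout, but which one depends on that unit.

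Appendix 10.1 is adapted from two publications not available here, so the pair may have been copied from them. The protocol would still need to say which number governs.

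**Conclusion.** The concern holds. By the protocol's own conversion the two figures are 0.9 mg/dL apart, about 8%. Rounding does not account for the difference, and no other section of the protocol or SAP resolves it. The classification is undetermined for corrected calcium above 10.6 and up to 11.5 mg/dL (2.65 to 2.875 mmol/L).

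The exposed endpoints are PFS, duration of response and duration of MRD response, together with the rule for stopping at progression. MTD and DLT are not affected. How many patients would fall in the band and depend on this criterion alone cannot be estimated from the documents. The conclusion rests on the 7.0 / 1.75 pair in Appendix 10.3; only the worked case needs the albumin correction. Which threshold is clinically right is not settled here.

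**What to change.** In Section 5.1.2.6 and the progressive disease row of Appendix 10.1, print one threshold in matching units after checking the cited source. The choice is 11.5 mg/dL (2.875 mmol/L; 2.87 or 2.88 to two decimals) or 10.6 mg/dL (2.65 mmol/L). Put the same pair in the clinical relapse row, and correct the creatinine unit there at the same time.

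In the SAP, name one correction formula. List every progression called on hypercalcaemia and every corrected calcium above 10.6 and up to 11.5 mg/dL, each checked against the single threshold. The listing is for review: attribution and response assessment stay with the investigator and should not be overridden by program. If only one change is made, it should be the correction to the protocol text.

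The cost is one corrected figure in two places, a third for consistency, and one listing. Total calcium and albumin are already collected (Sections 5.1.2.1 and 5.2.4.1). Changing the protocol text means an amendment, with the approvals in Section 8.1. It cannot undo a treatment stop already made.

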5.1.2.7 Progression free survival (PFS)

PFS is defined as the time from first treatment with BI 836909 until disease progression or death.

Proprietary confidential information.

© 2018 Boehringer Ingelheim International GmbH or one or more of its affiliated companies. All rights reserved.

This document may not - in full or in part - be passed on, reproduced, published or otherwise used without prior written permission.

5.2 SAFETY

5.2.1 Endpoint(s) of safety

The primary objective is to assess the safety of the drug in humans and to determine the MTD of BI 836909.

Primary Endpoints are the following:

- Maximum tolerated dose (MTD) of BI 836909
MTD is defined as the highest dose level tested where ≤ 1 patient out of 6 develop dose limiting toxicity. If MTD cannot be determined based on safety findings, a recommended dose for further development will be determined based on pharmacokinetic and pharmacodynamic data.
The MTD will be defined on the basis of DLT observed during cycle 1. However, for those patients who receive more than one cycle of BI 836909, all adverse events corresponding to the definition of DLT ([Section 5.2.1.1](#)) will be considered for the purpose of confirming the MTD and for the selection of the recommended dose for further development. In regular intervals, all available safety data including adverse events qualifying for DLT will be reviewed by the safety committee.
- Number of patients with dose limiting toxicities

The safety of BI 836909 will be assessed by a descriptive analysis of incidence and intensity of adverse events graded according to CTCAE (version 4.03), the incidence dose limiting toxicity (DLT), laboratory data and results of physical examination.

Further endpoint of safety is

- Immunogenicity of BI 836909 (frequency of patients developing anti-drug antibodies)

The safety data will be reviewed in regular intervals as well as ad hoc if needed.

The safety endpoints will be assessed in a descriptive way without confirmatory analyses.

5.2.1.1 Dose limiting toxicity

Dose limiting toxicity (DLT) is defined as any drug-related non-haematological adverse event CTCAE version 4.03 grade 3 or higher. The following grade 3 events will not be considered

Proprietary confidential information.

© 2018 Boehringer Ingelheim International GmbH or one or more of its affiliated companies. All rights reserved.

This document may not - in full or in part - be passed on, reproduced, published or otherwise used without prior written permission.

DLT: febrile neutropenia and infection responding to antibiotic/anti-infective treatment within 48 hours, fatigue, headache, insomnia, fever, hypotension.

Laboratory parameters of grade ≥ 3 but not considered clinically relevant and/or responding to routine medical management, will not be considered dose limiting toxicities.

Additional events that are considered DLT include:

- Persistent grade 4 neutropenia or thrombocytopenia until day 56 in the absence of detectable Multiple Myeloma as it may reflect a marrow toxic effect of BI 836909.

If infusion related reactions (IRR) or cytokine release syndromes (CRS) \geq grade 2 occur or constitute DLT events the safety committee may decide to switch to step dosing for the respective and any higher dose cohort. In that case the infusion will be started at 10(-30)% of the target dose on day 1 of the course and will be escalated to the full target dose from day 9 of course 1 on for the remainder of the course. Patients will be hospitalized and pre-medicated for the dose increase the same way they are for start of treatment. Once the safety committee decides to switch to step dosing patients that may have developed DLT due to IRR or CRS events may be replaced at the respective cohort by additional patients who will receive treatment with the adapted administration schedule (step dosing).

Although hematological adverse events (e.g. anemia, thrombocytopenia, neutropenia, lymphopenia) will not be considered DLT, complications resulting from hematological events, e.g. bleeding due to thrombocytopenia or grade 4 infection due to neutropenia are classified as non-hematological adverse events and are covered by the above definition of DLT. Nevertheless, hematological adverse events will be considered for definition of the dose for further development.

